## **10 Pharmacokinetic Analysis**

Not applicable.

## **11 Pharmacodynamic Analysis**

Not applicable.

## **12 Pharmacogenomic Analysis**

Not applicable.

## **13 Interim Analysis**

Not applicable.

## **14 Changes in the Planned Analyses**

The following calculations specified in [Section 7.6.2](#) in the protocol were not performed.

- The number and percentage of subjects who are in the potentially clinically significant range will be calculated.

## **15 References**

None.

## Appendix 1 Criteria for Vital Signs Potential Clinical Significance

Variable	CRITERIA 1	CRITERIA 2
DIASTOLIC BLOOD PRESSURE (mmHg)	DIASTOLIC BLOOD PRESSURE (mmHg) <50 AND DECREASE $\geq 15$	DIASTOLIC BLOOD PRESSURE (mmHg) >105 AND INCREASE $\geq 15$
PULSE RATE (beats/min)	PULSE RATE (BPM) <50 AND DECREASE $\geq 15$	PULSE RATE (BPM) >120 AND INCREASE $\geq 15$
SYSTOLIC BLOOD PRESSURE (mmHg)	SYSTOLIC BLOOD PRESSURE (mmHg) <90 AND DECREASE $\geq 20$	SYSTOLIC BLOOD PRESSURE (mmHg) >180 AND INCREASE $\geq 20$
TEMPERATURE (°C)		TEMPERATURE (°C) $\geq 37.8$ AND INCREASE $\geq 1.1^\circ\text{C}$
WEIGHT (kg)	WEIGHT (kg) DECREASE $\geq 7\%$	WEIGHT (kg) INCREASE $\geq 7\%$

The potential Hy's Law Cases are defined as subjects with the following criteria:  
ALT $\geq$ 3xULN (OR SCREENING VALUE) OR AST $\geq$ 3xULN (OR SCREENING VALUE)  
AND BILIRUBIN $\geq$ 2xULN (OR SCREENING VALUE)

Appendix 3	List of Summary Tables
CT-1	Subject Disposition
CT-2	Reasons for Discontinuation
CT-3.1	Demographic Characteristics Safety Set
CT-3.2	Demographic Characteristics Efficacy Set
CT-4.1	Concomitant Medications: Medications Taken Prior to Start of Study Therapy
CT-4.2	Concomitant Medications: Medications Taken During Study Therapy
CT-4.3	Concomitant Medications: Medications Taken After Study Therapy
CT-5.1.1	Analysis of Responder Rate for Overall IGA Score
CT-5.1.2	Supplementary Analysis of Responder Rate for Overall IGA Score - LOCF
CT-5.1.3	Supplementary Analysis of Responder Rate for Overall IGA Score - OC
CT-5.1.4	Analysis of Responder Rate for Overall IGA Score - Revised Responder Definition
CT-5.1.5	Shift Tables of Overall IGA Score - OC
CT-5.1.6	Shift Tables of Overall IGA Score - LOCF
CT-5.2.1	Analysis of 75% Over Responder Rate for Overall EASI Score
CT-5.2.2	Analysis of 90% Over Responder Rate for Overall EASI Score
CT-5.2.3	Analysis of 50% Over Responder Rate for Overall EASI Score
CT-5.3.1	Analysis of Baseline and Change from Baseline in Overall IGA Score - MMRM
CT-5.3.2	Analysis of Baseline and Change from Baseline in Overall IGA Score - ANCOVA OC
CT-5.3.3	Analysis of Baseline and Change from Baseline in Overall IGA Score - ANCOVA LOCF
CT-5.4.1.1	Analysis of Baseline and Change from Baseline in Overall EASI Score - MMRM
CT-5.4.1.2	Analysis of Baseline and Change from Baseline in Overall EASI Score - ANCOVA OC

- CT-5.4.1.3 Analysis of Baseline and Change from Baseline in Overall EASI Score - ANCOVA LOCF
- CT-5.4.1.4 Analysis of Baseline and Percent Change from Baseline in Overall EASI Score - MMRM
- CT-5.4.1.5 Analysis of Baseline and Percent Change from Baseline in Overall EASI Score - ANCOVA OC
- CT-5.4.1.6 Analysis of Baseline and Percent Change from Baseline in Overall EASI Score - ANCOVA LOCF
- CT-5.4.2.1 Analysis of Baseline and Change from Baseline in Overall EASI Score, Erythema - MMRM
- CT-5.4.2.2 Analysis of Baseline and Change from Baseline in Overall EASI Score, Erythema - ANCOVA OC
- CT-5.4.2.3 Analysis of Baseline and Change from Baseline in Overall EASI Score, Erythema - ANCOVA LOCF
- CT-5.4.2.4 Analysis of Baseline and Percent Change from Baseline in Overall EASI Score, Erythema - MMRM
- CT-5.4.2.5 Analysis of Baseline and Percent Change from Baseline in Overall EASI Score, Erythema - ANCOVA OC
- CT-5.4.2.6 Analysis of Baseline and Percent Change from Baseline in Overall EASI Score, Erythema - ANCOVA LOCF
- CT-5.4.3.1 Analysis of Baseline and Change from Baseline in Overall EASI Score, Induration/Papulation - MMRM
- CT-5.4.3.2 Analysis of Baseline and Change from Baseline in Overall EASI Score, Induration/Papulation - ANCOVA OC
- CT-5.4.3.3 Analysis of Baseline and Change from Baseline in Overall EASI Score, Induration/Papulation - ANCOVA LOCF
- CT-5.4.3.4 Analysis of Baseline and Percent Change from Baseline in Overall EASI Score, Induration/Papulation - MMRM
- CT-5.4.3.5 Analysis of Baseline and Percent Change from Baseline in Overall EASI Score, Induration/Papulation - ANCOVA OC
- CT-5.4.3.6 Analysis of Baseline and Percent Change from Baseline in Overall EASI Score, Induration/Papulation - ANCOVA LOCF

- CT-5.4.4.1 Analysis of Baseline and Change from Baseline in Overall EASI Score, Excoriation - MMRM
- CT-5.4.4.2 Analysis of Baseline and Change from Baseline in Overall EASI Score, Excoriation - ANCOVA OC
- CT-5.4.4.3 Analysis of Baseline and Change from Baseline in Overall EASI Score, Excoriation - ANCOVA LOCF
- CT-5.4.4.4 Analysis of Baseline and Percent Change from Baseline in Overall EASI Score, Excoriation - MMRM
- CT-5.4.4.5 Analysis of Baseline and Percent Change from Baseline in Overall EASI Score, Excoriation - ANCOVA OC
- CT-5.4.4.6 Analysis of Baseline and Percent Change from Baseline in Overall EASI Score, Excoriation - ANCOVA LOCF
- CT-5.4.5.1 Analysis of Baseline and Change from Baseline in Overall EASI Score, Lichenification - MMRM
- CT-5.4.5.2 Analysis of Baseline and Change from Baseline in Overall EASI Score, Lichenification - ANCOVA OC
- CT-5.4.5.3 Analysis of Baseline and Change from Baseline in Overall EASI Score, Lichenification - ANCOVA LOCF
- CT-5.4.5.4 Analysis of Baseline and Percent Change from Baseline in Overall EASI Score, Lichenification - MMRM
- CT-5.4.5.5 Analysis of Baseline and Percent Change from Baseline in Overall EASI Score, Lichenification - ANCOVA OC
- CT-5.4.5.6 Analysis of Baseline and Percent Change from Baseline in Overall EASI Score, Lichenification - ANCOVA LOCF
- CT-5.4.6.1 Analysis of Baseline and Change from Baseline in Overall EASI Score, HEAD/NECK - MMRM
- CT-5.4.6.2 Analysis of Baseline and Change from Baseline in Overall EASI Score, HEAD/NECK - ANCOVA OC
- CT-5.4.6.3 Analysis of Baseline and Change from Baseline in Overall EASI Score, HEAD/NECK - ANCOVA LOCF
- CT-5.4.6.4 Analysis of Baseline and Percent Change from Baseline in Overall EASI Score, HEAD/NECK - MMRM

- CT-5.4.6.5 Analysis of Baseline and Percent Change from Baseline in Overall EASI Score, HEAD/NECK - ANCOVA OC
- CT-5.4.6.6 Analysis of Baseline and Percent Change from Baseline in Overall EASI Score, HEAD/NECK - ANCOVA LOCF
- CT-5.4.7.1 Analysis of Baseline and Change from Baseline in Overall EASI Score, UPPER LIMBS - MMRM
- CT-5.4.7.2 Analysis of Baseline and Change from Baseline in Overall EASI Score, UPPER LIMBS - ANCOVA OC
- CT-5.4.7.3 Analysis of Baseline and Change from Baseline in Overall EASI Score, UPPER LIMBS - ANCOVA LOCF
- CT-5.4.7.4 Analysis of Baseline and Percent Change from Baseline in Overall EASI Score, UPPER LIMBS - MMRM
- CT-5.4.7.5 Analysis of Baseline and Percent Change from Baseline in Overall EASI Score, UPPER LIMBS - ANCOVA OC
- CT-5.4.7.6 Analysis of Baseline and Percent Change from Baseline in Overall EASI Score, UPPER LIMBS - ANCOVA LOCF
- CT-5.4.8.1 Analysis of Baseline and Change from Baseline in Overall EASI Score, TRUNK - MMRM
- CT-5.4.8.2 Analysis of Baseline and Change from Baseline in Overall EASI Score, TRUNK - ANCOVA OC
- CT-5.4.8.3 Analysis of Baseline and Change from Baseline in Overall EASI Score, TRUNK - ANCOVA LOCF
- CT-5.4.8.4 Analysis of Baseline and Percent Change from Baseline in Overall EASI Score, TRUNK - MMRM
- CT-5.4.8.5 Analysis of Baseline and Percent Change from Baseline in Overall EASI Score, TRUNK - ANCOVA OC
- CT-5.4.8.6 Analysis of Baseline and Percent Change from Baseline in Overall EASI Score, TRUNK - ANCOVA LOCF
- CT-5.4.9.1 Analysis of Baseline and Change from Baseline in Overall EASI Score, LOWER LIMBS - MMRM
- CT-5.4.9.2 Analysis of Baseline and Change from Baseline in Overall EASI Score, LOWER LIMBS - ANCOVA OC

CT-5.4.9.3 Analysis of Baseline and Change from Baseline in Overall EASI Score, LOWER LIMBS - ANCOVA LOCF

CT-5.4.9.4 Analysis of Baseline and Percent Change from Baseline in Overall EASI Score, LOWER LIMBS - MMRM

CT-5.4.9.5 Analysis of Baseline and Percent Change from Baseline in Overall EASI Score, LOWER LIMBS - ANCOVA OC

CT-5.4.9.6 Analysis of Baseline and Percent Change from Baseline in Overall EASI Score, LOWER LIMBS - ANCOVA LOCF

CT-5.5.1 Analysis of Baseline and Change from Baseline in VRS for Pruritus Score - MMRM

CT-5.5.2 Analysis of Baseline and Change from Baseline in VRS for Pruritus Score - ANCOVA OC

CT-5.5.3 Analysis of Baseline and Change from Baseline in VRS for Pruritus Score - ANCOVA LOCF

CT-5.5.4 Analysis of Baseline and Change from Baseline in VRS for Pruritus Score (Week 1) - MMRM

CT-5.5.5 Analysis of Baseline and Change from Baseline in VRS for Pruritus Score (Week 1) - ANCOVA OC

CT-5.6.1 Analysis of Baseline and Change from Baseline in POEM Score - MMRM

CT-5.6.2 Analysis of Baseline and Change from Baseline in POEM Score - ANCOVA OC

CT-5.6.3 Analysis of Baseline and Change from Baseline in POEM Score - ANCOVA LOCF

CT-5.6.4 Analysis of Baseline and Percent Change from Baseline in POEM Score - MMRM

CT-5.6.5 Analysis of Baseline and Percent Change from Baseline in POEM Score - ANCOVA OC

CT-5.6.6 Analysis of Baseline and Percent Change from Baseline in POEM Score - ANCOVA LOCF

CT-5.7.1 Analysis of Baseline and Change from Baseline in Overall Percentage Affected Body Surface Area - MMRM

- CT-5.7.2 Analysis of Baseline and Change from Baseline in Overall Percentage Affected Body Surface Area - ANCOVA OC
- CT-5.7.3 Analysis of Baseline and Change from Baseline in Overall Percentage Affected Body Surface Area - ANCOVA LOCF
- CT-6.1.1 Subgroup Analysis of Responder Rate for Overall IGA Score - by Age
- CT-6.1.2 Subgroup Analysis of Responder Rate for Overall IGA Score - by Sex
- CT-6.1.3 Subgroup Analysis of Responder Rate for Overall IGA Score - by IGA Score at Baseline
- CT-6.1.4 Subgroup Analysis of Responder Rate for Overall IGA Score - by Severity of Atopic Dermatitis
- CT-6.1.5 Subgroup Analysis of Responder Rate for Overall IGA Score - by Total EASI Score at Baseline (<15, 15=<)
- CT-6.1.6 Subgroup Analysis of Responder Rate for Overall IGA Score - by Affected Body Surface Area (<20%, 20%=<)
- CT-6.2.1 Subgroup Analysis of 75% Over Responder Rate for Overall EASI Score - by Age
- CT-6.2.2 Subgroup Analysis of 75% Over Responder Rate for Overall EASI Score - by Sex
- CT-6.2.3 Subgroup Analysis of 75% Over Responder Rate for Overall EASI Score - by IGA Score at Baseline
- CT-6.2.4 Subgroup Analysis of 75% Over Responder Rate for Overall EASI Score - by Severity of Atopic Dermatitis
- CT-6.2.5 Subgroup Analysis of 75% Over Responder Rate for Overall EASI Score - by Total EASI Score at Baseline (<15, 15=<)
- CT-6.2.6 Subgroup Analysis of 75% Over Responder Rate for Overall EASI Score - by Affected Body Surface Area (<20%, 20%=<)
- CT-6.3.1 Exploratory Analysis of Impact of Age Factor to efficacy by Logistic Analysis -by Age (Continual)
- CT-6.3.2 Exploratory Analysis of Impact of Age Factor to efficacy by Logistic Analysis -by Age (2-6 Years, 7-14 Years)
- CT-7.1.1 Summary of Treatment Compliance

- CT-7.1.2 Summary of Treatment Compliance for Number of Administrations
- CT-7.2.1 Extent of Exposure to Trial Medication
- CT-7.2.2 Summary of Exposure
- CT-8.1.1 Adverse Events (All Causalities)
- CT-8.1.2 Adverse Events According to Application Site (All Causalities)
- CT-8.2.1.1 Incidence of Treatment-emergent Adverse Events by System Organ Class
- CT-8.2.1.2 Incidence of Treatment-emergent Adverse Events by System Organ Class
- CT-8.2.1.3 Incidence of Treatment-emergent Adverse Events by System Organ Class
- CT-8.2.2.1 Incidence of Treatment-emergent Adverse Events by System Organ Class and Preferred Term
- CT-8.2.2.2 Incidence of Treatment-emergent Adverse Events by System Organ Class and Preferred Term
- CT-8.2.2.3 Incidence of Treatment-emergent Adverse Events by System Organ Class and Preferred Term
- CT-8.2.3.1 Incidence of Treatment-emergent Adverse Events by System Organ Class, Preferred Term and Severity
- CT-8.2.3.2 Incidence of Treatment-emergent Adverse Events by System Organ Class, Preferred Term and Severity
- CT-8.2.3.3 Incidence of Treatment-emergent Adverse Events by System Organ Class, Preferred Term and Severity
- CT-8.2.4.1 Incidence of Treatment-emergent Adverse Events by System Organ Class, Preferred Term and CTCAE Grade
- CT-8.2.4.2 Incidence of Treatment-emergent Adverse Events by System Organ Class, Preferred Term and CTCAE Grade
- CT-8.2.4.3 Incidence of Treatment-emergent Adverse Events by System Organ Class, Preferred Term and CTCAE Grade
- CT-8.3.1.1 Incidence of Potentially Drug-Related Treatment-emergent Adverse Events by System Organ Class
- CT-8.3.1.2 Incidence of Potentially Drug-Related Treatment-emergent Adverse Events by System Organ Class

- CT-8.3.1.3 Incidence of Potentially Drug-Related Treatment-emergent Adverse Events by System Organ Class
- CT-8.3.2.1 Incidence of Potentially Drug-Related Treatment-emergent Adverse Events by System Organ Class and Preferred Term
- CT-8.3.2.2 Incidence of Potentially Drug-Related Treatment-emergent Adverse Events by System Organ Class and Preferred Term
- CT-8.3.2.3 Incidence of Potentially Drug-Related Treatment-emergent Adverse Events by System Organ Class and Preferred Term
- CT-8.3.3.1 Incidence of Potentially Drug-related Treatment-emergent Adverse Events by System Organ Class, Preferred Term and Severity
- CT-8.3.3.2 Incidence of Potentially Drug-related Treatment-emergent Adverse Events by System Organ Class, Preferred Term and Severity
- CT-8.3.3.3 Incidence of Potentially Drug-related Treatment-emergent Adverse Events by System Organ Class, Preferred Term and Severity
- CT-8.3.4.1 Incidence of Potentially Drug-related Treatment-emergent Adverse Events by System Organ Class, Preferred Term and CTCAE Grade
- CT-8.3.4.2 Incidence of Potentially Drug-related Treatment-emergent Adverse Events by System Organ Class, Preferred Term and CTCAE Grade
- CT-8.3.4.3 Incidence of Potentially Drug-related Treatment-emergent Adverse Events by System Organ Class, Preferred Term and CTCAE Grade
- CT-8.4.1.1 Incidence of Deaths due to Treatment-emergent Adverse Events by System Organ Class
- CT-8.4.1.2 Incidence of Deaths due to Treatment-emergent Adverse Events by System Organ Class
- CT-8.4.1.3 Incidence of Deaths due to Treatment-emergent Adverse Events by System Organ Class
- CT-8.4.2.1 Incidence of Deaths due to Treatment-emergent Adverse Events by System Organ Class and Preferred Term
- CT-8.4.2.2 Incidence of Deaths due to Treatment-emergent Adverse Events by System Organ Class and Preferred Term
- CT-8.4.2.3 Incidence of Deaths due to Treatment-emergent Adverse Events by System Organ Class and Preferred Term

- CT-8.5.1.1 Incidence of Serious Treatment-emergent Adverse Events by System Organ Class
- CT-8.5.1.2 Incidence of Serious Treatment-emergent Adverse Events by System Organ Class
- CT-8.5.1.3 Incidence of Serious Treatment-emergent Adverse Events by System Organ Class
- CT-8.5.2.1 Incidence of Serious Treatment-emergent Adverse Events by System Organ Class and Preferred Term
- CT-8.5.2.2 Incidence of Serious Treatment-emergent Adverse Events by System Organ Class and Preferred Term
- CT-8.5.2.3 Incidence of Serious Treatment-emergent Adverse Events by System Organ Class and Preferred Term
- CT-8.5.3.1 Incidence of Serious Treatment-emergent Adverse Events by System Organ Class, Preferred Term and Severity
- CT-8.5.3.2 Incidence of Serious Treatment-emergent Adverse Events by System Organ Class, Preferred Term and Severity
- CT-8.5.3.3 Incidence of Serious Treatment-emergent Adverse Events by System Organ Class, Preferred Term and Severity
- CT-8.5.4.1 Incidence of Serious Treatment-emergent Adverse Events by System Organ Class, Preferred Term and CTCAE Grade
- CT-8.5.4.2 Incidence of Serious Treatment-emergent Adverse Events by System Organ Class, Preferred Term and CTCAE Grade
- CT-8.5.4.3 Incidence of Serious Treatment-emergent Adverse Events by System Organ Class, Preferred Term and CTCAE Grade
- CT-8.6.1.1 Incidence of Treatment-emergent Adverse Events Resulting in Discontinuation from Study by System Organ Class
- CT-8.6.1.2 Incidence of Treatment-emergent Adverse Events Resulting in Discontinuation from Study by System Organ Class
- CT-8.6.1.3 Incidence of Treatment-emergent Adverse Events Resulting in Discontinuation from Study by System Organ Class
- CT-8.6.2.1 Incidence of Treatment-emergent Adverse Events Resulting in Discontinuation from Study by System Organ Class and Preferred Term

- CT-8.6.2.2 Incidence of Treatment-emergent Adverse Events Resulting in Discontinuation from Study by System Organ Class and Preferred Term
- CT-8.6.2.3 Incidence of Treatment-emergent Adverse Events Resulting in Discontinuation from Study by System Organ Class and Preferred Term
- CT-8.6.3.1 Incidence of Treatment-emergent Adverse Events Resulting in Discontinuation from Study by System Organ Class, Preferred Term and Severity
- CT-8.6.3.2 Incidence of Treatment-emergent Adverse Events Resulting in Discontinuation from Study by System Organ Class, Preferred Term and Severity
- CT-8.6.3.3 Incidence of Treatment-emergent Adverse Events Resulting in Discontinuation from Study by System Organ Class, Preferred Term and Severity
- CT-8.6.4.1 Incidence of Treatment-emergent Adverse Events Resulting in Discontinuation from Study by System Organ Class, Preferred Term and CTCAE Grade
- CT-8.6.4.2 Incidence of Treatment-emergent Adverse Events Resulting in Discontinuation from Study by System Organ Class, Preferred Term and CTCAE Grade
- CT-8.6.4.3 Incidence of Treatment-emergent Adverse Events Resulting in Discontinuation from Study by System Organ Class, Preferred Term and CTCAE Grade
- CT-8.7.1.1 Incidence of Treatment-emergent Adverse Events Greater Than or Equal to 5% in Any Group by System Organ Class and Preferred Term
- CT-8.7.1.2 Incidence of Treatment-emergent Adverse Events Greater Than or Equal to 5% in Any Group by System Organ Class and Preferred Term
- CT-8.7.1.3 Incidence of Treatment-emergent Adverse Events Greater Than or Equal to 5% in Any Group by System Organ Class and Preferred Term
- CT-8.8.1.1 Incidence of Non-Serious Treatment-emergent Adverse Events Greater Than or Equal to 5% in Any Group by System Organ Class and Preferred Term

- CT-8.8.1.2 Incidence of Non-Serious Treatment-emergent Adverse Events Greater Than or Equal to 5% in Any Group by System Organ Class and Preferred Term
- CT-8.8.1.3 Incidence of Non-Serious Treatment-emergent Adverse Events Greater Than or Equal to 5% in Any Group by System Organ Class and Preferred Term
- CT-8.9.1.1 Incidence of Treatment-emergent Adverse Events by System Organ Class and Preferred Term According to Application Site
- CT-8.9.1.2 Incidence of Treatment-emergent Adverse Events by System Organ Class and Preferred Term According to Application Site
- CT-8.9.1.3 Incidence of Treatment-emergent Adverse Events by System Organ Class and Preferred Term According to Application Site
- CT-8.10.1.1 Incidence of Potentially Drug-related Treatment-emergent Adverse Events by System Organ Class and Preferred Term According to Application Site
- CT-8.10.1.2 Incidence of Potentially Drug-related Treatment-emergent Adverse Events by System Organ Class and Preferred Term According to Application Site
- CT-8.10.1.3 Incidence of Potentially Drug-related Treatment-emergent Adverse Events by System Organ Class and Preferred Term According to Application Site
- CT-9.1 Listing of Deaths
- CT-9.2 Listing of Serious Adverse Events
- CT-9.3 Listing of Study Drug Discontinuations Due to Adverse Events
- CT-9.4 Incidence of Potential Hy's Law Cases
- CT-9.5 Listing of Potential Hy's Law Cases - by Subject
- CT-10.1.1 Mean Change From Baseline in Laboratory Test Values: Serum Chemistry
- CT-10.1.2 Mean Change From Baseline in Laboratory Test Values: Hematology
- CT-10.2.1 Shift Tables of Clinical Laboratory Test Results: Serum Chemistry
- CT-10.2.2 Shift Tables of Clinical Laboratory Test Results: Hematology
- CT-10.2.3 Shift Tables of Clinical Laboratory Test Results: Urinalysis
- CT-11.1 Mean Change From Baseline in Vital Sign Parameters
- CT-11.2 Listing of Vital Signs Abnormalities

- CT-11.3 Incidence of Potential Clinical Significance in Vital Signs
- CT-11.4 Criteria for Vital Signs Potential Clinical Significance
  
- CF-1.0 Responder Rate for Overall IGA Score by Visit
- CF-1.1 Incidence of Responder Rate for Overall IGA Score by Visit
- CF-1.2 Incidence of 75% Over Responder Rate for Overall EASI Score by Visit
- CF-1.3 Incidence of 90% Over Responder Rate for Overall EASI Score by Visit
- CF-1.4 Incidence of 50% Over Responder Rate for Overall EASI Score by Visit
- CF-1.5 Incidence of Responder Rate for Overall IGA Score by Visit - Less Than 7 Years
- CF-1.6 Incidence of Responder Rate for Overall IGA Score by Visit - Greater Than or Equal to 7 Years
- CF-2.1 Least Square Means of Change from Baseline in Overall IGA Score by Visit - MMRM
- CF-2.2 Least Square Means of Change from Baseline in Overall EASI Score by Visit - MMRM

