When OPA-15406 ointment was administered to rats and miniature pigs, the dermal absorption of OPA-15406 was low. When ¹⁴C-labeled OPA-15406 ointment (¹⁴C-OPA-15406) was administered percutaneously in rats, the absorbed radioactivity was distributed through various tissues of the body, but the level of radioactivity in the central nervous system (cerebrum and cerebellum) was lower than that in plasma. Several metabolites were identified in human plasma and urine collected in the phase 1 trial in Japan (Trial 271-14-001), but it was judged that there are no human-specific metabolites since all metabolites were detected in animal plasma. The main excretion route of radioactivity was biliary excretion and fecal elimination. The in vitro protein binding rates of ¹⁴C-OPA-15406 in human and animal serum were high (>99%). OPA-15406 (and its metabolites) did not readily bind to melanin.

Cytochrome P450 (CYP) 1A2 and CYP3A4 were involved in the metabolism of OPA-15406. OPA-15406 directly inhibited CYP1A2, CYP2B6, CYP2C8, CYP2C9, CYP2C19 and CYP2D6 (K_i : 1.284 - 8.833 mol/L) and showed metabolism-dependent inhibition of CYP2B6 and CYP3A4. The pharmacokinetic interaction risk of OPA-15406 is considered to be low since K_i values were much higher than the plasma exposure in the clinical trial. On the other hand, OPA 15406 showed an inducing effect on CYP1A2, CYP2B6 and CYP3A4.

In the 4, 13 and 26-week repeated-dose percutaneous toxicity studies in rats, OPA-15406 ointment was administered to intact skin (open cutaneous) once daily. As a result, no changes associated with the test substance were observed at the administration sites in any OPA-15406 ointment (vehicle, 0.1%, 0.3%, 1% and 3%) groups. Although suppressed weight increase was observed, it was not exacerbated in a prolonged treatment period. The no observed adverse effect level (NOAEL) for systemic toxicity in the 26 week repeated-dose percutaneous toxicity study was estimated to be 2.95 mg/kg (1% ointment) in the male rats and 1.07 mg/kg (0.3% ointment) in the female rats.

In the 4, 13 and 39-week repeated-dose percutaneous toxicity studies in miniature pigs, OPA-15406 ointment was administered to intact or abraded skin (open cutaneous) once daily. As a result, no changes associated with the test substance were observed in any

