3.4.2 Inclusion Criteria

Subjects are required to meet the following inclusion criteria #1 through #7 in [Table 3.4.2-1](#) at the screening examination, and #6 and #7 at the screening examination and the baseline examination.

Table 3.4.2-1 Inclusion Criteria	
1	Sex: Either male or female
2	Hospitalization status: Outpatient
3	Age: 2 to 14 years, inclusive (at time of obtaining informed consent)
4	Able to obtain written informed consent from the subject's legal guardian
5	Diagnosis of AD based on the Japanese Dermatological Association's criteria ¹ (refer to Appendix 1)
6	Atopic dermatitis affecting $\geq 5\%$ to $\leq 40\%$ of BSA (excluding scalp)
7	IGA score of 2 or 3

[Rationale for Inclusion Criteria]

- 1) Atopic dermatitis occurs in both males and females.
- 2) Most patients to be included in this trial are outpatients.
- 3) The phase 2 trial (Trial 271-102-00002) in Japan was conducted in pediatric patients (aged 2 - 14 years old), showing efficacy OPA-15406 ointment without no particular safety concerns. Therefore, subjects aged 2 to 14 years old are included in the present trial.
- 4) To conduct the trial without any ethical problems.
- 5) Patients with AD who meet the Japanese Dermatological Association's criteria are included in order to evaluate the efficacy and safety of the IMP in AD patients in Japan.
- 6)-7) To appropriately evaluate the efficacy of the IMP on the target disease.

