### **3.3 Trial Population**

The target population of this trial is pediatric AD patients with an IGA score of 2 or 3. Subjects will be included in the trial to reach the target number of 240 subjects for IMP administration (the target inclusion ratio of “2 to 6 years old” to “7 to 14 years old” of age is 1:1). Any withdrawal will not be supplemented.

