### **9.4 Vital Signs and Body Weight**

For body weight, body temperature, blood pressure (systolic and diastolic), and pulse rate, the descriptive statistics will be calculated for measured values and changes from baseline at each timepoint by treatment group. The number and percentage of subjects with clinically abnormal changes (Appendix 1) in body temperature, blood pressure (systolic and diastolic), and pulse rate will be calculated by treatment group and for all subjects. For clinically abnormal changes, all data after starting administration, except for baseline or missing timepoints, will be included in the evaluation. Also, a list of subjects with clinically abnormal changes will be created.

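### Blood pressure flagging limits without age bands leave the high blood pressure count nearly uninformative at ages 2-14, and body weight drops out of the abnormal-change count without being declared

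*SAP*

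**What the plan says.** Protocol 3.4.2 sets eligibility as "Age: 2 to 14 years, inclusive (at time of obtaining informed consent"). SAP 3.3 plans to "reach the target number of 240 subjects for IMP administration", with a 1:1 target for ages 2-6 and 7-14.

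SAP Appendix 1 gives one row per vital sign and no age bands. Each blood pressure and pulse rule needs an absolute limit and a minimum change together. The high-side rules are:

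- Systolic: "SYSTOLIC BLOOD PRESSURE (mmHg) >180 AND INCREASE" of at least 20 mmHg.
- Diastolic: "DIASTOLIC BLOOD PRESSURE (mmHg) >105 AND INCREASE" of at least 15 mmHg.
- Pulse: "PULSE RATE (BPM) >120 AND INCREASE" of at least 15 beats per minute.

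Appendix 1 also has a temperature rule (37.8 °C or above with a rise of at least 1.1 °C) and a weight rule (7% either way).

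SAP 9.4 counts "The number and percentage of subjects with clinically abnormal changes (Appendix 1) in body temperature, blood pressure (systolic and diastolic), and pulse rate", by treatment group and overall, and lists the subjects flagged. Weight appears in 9.4 only in the descriptive statistics. Protocol 7.6.3, whose title covers vital signs and body weight, plans the abnormal-change count without excluding any variable. SAP section 14 declares one departure from the protocol, and it concerns laboratory tests under protocol 7.6.2.

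**The concern.** Vital signs and body weight are named safety endpoints (Protocol 3.5.3), and the incidence of abnormal values is a listed output (SAP Appendix 3, CT-11.3). Protocol 2.1 says the recommended dose should be settled by weighing risk and benefit by age as well as overall. If the absolute blood pressure limits lie far above where children start, the high-side count will be about zero in every arm whether or not some children have large rises. A reader could then take a row of zeros as reassurance that it cannot give.

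The weight point is one of consistency. A criterion is defined, the protocol plans a count under a title that includes weight, and the SAP's count leaves weight out without saying so.

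**Working it through.** The plan states no figure to reproduce here, so the check is how far a child must move to be flagged.

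**Inputs.** The limits and minimum changes come from SAP Appendix 1. The baselines are assumptions, because the documents give no paediatric ranges: systolic 80-120 mmHg, diastolic 45-75 mmHg and pulse 70-100 beats per minute, chosen wide.

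**Formula.** The rise needed is the larger of (limit − baseline) and the minimum change. Where the limit governs, the rise must exceed that difference.

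| Rule | Baseline | Limit − baseline | Rise needed | As % of baseline |
|---|---|---|---|---|
| Systolic | 80 | 180 − 80 | >100 | 125% |
| Systolic | 100 | 180 − 100 | >80 | 80% |
| Systolic | 120 | 180 − 120 | >60 | 50% |
| Diastolic | 45 | 105 − 45 | >60 | 133% |
| Diastolic | 60 | 105 − 60 | >45 | 75% |
| Diastolic | 75 | 105 − 75 | >30 | 40% |
| Pulse | 70 | 120 − 70 | >50 | 71% |
| Pulse | 100 | 120 − 100 | >20 | 20% |

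**Does the change condition do any work?** It governs only from a baseline of 180 − 20 = 160 mmHg systolic or 105 − 15 = 90 mmHg diastolic. Over the assumed baselines the absolute limit alone decides. The rise needed is 60/20 = 3 to 100/20 = 5 times the SAP's own systolic change value, and 30/15 = 2 to 60/15 = 4 times its diastolic one.

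**Pulse differs.** The crossover is 120 − 15 = 105 beats per minute. From about there upward a rise of 15 or slightly more is enough, so the pulse rule can fire.

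**Size of the younger stratum.** With a 1:1 age target, 240/2 = 120 subjects are aged 2-6, and 120/3 = 40 of them are in each arm.

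**Outputs affected.** The SAP 9.4 list of flagged subjects uses the same criteria as the count and inherits its blind spot. SAP 9.2 splits adverse events by age category, whereas 9.4 states no age split.

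**Weight, side by side.** This part needs no assumption.

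| Source | Treatment of weight |
|---|---|
| SAP Appendix 1 | Criterion given; weight is one of five variables |
| Protocol 7.6.3 | Count planned under vital signs and body weight, with no exclusion |
| SAP 9.4 | Count covers four variables (temperature, systolic, diastolic, pulse); weight absent |
| SAP section 14 | No mention |

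**The case against.** The strongest reply is that the gap is confined to one descriptive count. SAP 9.4 also plans values and changes at each timepoint by treatment group, weight included (CT-11.1), and PDATA-7 lists all vital signs by subject. A general shift in blood pressure would show in the mean changes. Protocol 1.2.9 reports no marked difference in vital signs among the groups of the earlier paediatric trial. All this stands and keeps the point minor. It does not rescue the count, because means can hide individual outliers and the flagged-subject listing depends on the same limits.

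It is also fair that the baselines come from outside the documents. The result is not sensitive to that choice, since even a baseline of 120 mmHg needs a rise above 60.

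The documents do not support several stronger readings that a reader might infer:

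- **The table cannot flag any real rise in a young child.** The pulse and temperature rules can be met; only the two blood pressure rows are close to inert. The limit "PULSE RATE (BPM) <50 AND DECREASE" of at least 15 is a low-side rule and says nothing about rises.
- **The low systolic and high pulse limits flood the table with ordinary variation.** Each also needs a minimum change: a systolic value below 90 counts only with a fall of at least 20 mmHg. No false-flag rate can be derived from the documents, and background flags would arise in all three randomised arms.
- **The rat data make the weight count important.** Protocol 1.1 says "Although suppressed weight increase was observed" but adds that it did not worsen with longer treatment. Slower weight gain need not appear as a 7% loss over 4 weeks. The planned mean change in weight is the more relevant output, so the case for the weight count rests on consistency alone.

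**Conclusion.** The point holds in two limited parts.

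First, the high blood pressure count and its listing are close to uninformative, because a flag needs a rise of more than 60-100 mmHg systolic or more than 30-60 mmHg diastolic. This rests on the assumed baselines. That the gap is widest at ages 2-6 rests on the further assumption that younger children start lower. How many abnormal values would be missed cannot be stated, because the documents give no age norms.

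Second, Appendix 1, SAP 9.4 and protocol 7.6.3 do not agree on weight, and section 14 is silent. Protocol 7.6.3 does not list the variables to be counted. But its title, together with the weight row in Appendix 1, makes inclusion the natural reading.

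This is a minor safety-reporting matter. It has no bearing on the primary analysis and does not mean that vital-sign reporting as a whole is blind to rises.

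**What to change.** Both changes should be fixed before unblinding.

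(a) **Blood pressure.** Either give Appendix 1 flagging limits specific to the SAP's own age bands (2-6 and 7-14), with their source stated, or add a change-only count using the SAP's own values of 20 mmHg systolic and 15 mmHg diastolic, by treatment group and age band. No replacement limits are proposed here, since the documents offer no basis for any. The change-only count should stand beside the Appendix 1 count and not replace it. SAP 9.4 evaluates all data after the start of administration, so each child has several chances to be flagged. The count will be noisy and should be read against vehicle.

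(b) **Weight.** Add body weight to the abnormal-change count in SAP 9.4, using the 7% criterion already in Appendix 1, so that the three places agree. Otherwise, declare the omission in SAP section 14.

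The cost is a short SAP edit, one table and one listing to reprogram, and more flags to review. No new data are needed.
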